Under the assumption that the true VE is 60%, the primary efficacy analysis will require ~160 confirmed COVID-19 illness cases which will provide 90% power to conclude the true VE is $> 30\%$. Assuming the placebo illness rate is 1.3%, ~17,600 subjects will be required in the evaluable efficacy population for the primary efficacy analyses. These calculations are based a one-sided Type I error rate of 0.025. Assuming 15% of the all-available efficacy population will be unevaluable for the evaluable efficacy population, ~20,700 subjects will be sufficient to accrue ~17,600 subjects in the evaluable efficacy population.

Dependent upon the evolution of the pandemic, it is possible that the COVID-19 illness rate may change as the study progresses. An increase in illness rate could accelerate case accrual allowing the primary endpoints to be evaluated sooner, whereas a decrease in illness rate could slow down case accrual delaying the evaluation. At the time of the first interim efficacy analysis, the independent statistical team and DMC will evaluate the placebo illness rate. If the upper bound of the two-sided 95% CI for the observed placebo illness rate is less than the assumed placebo illness rate, then the sample size will be re-estimated by the independent statistician and DMC based on the observed placebo illness rate, and recommendations made to the Sponsor for final decision by the Sponsor.

Primary Efficacy Analysis: The primary efficacy endpoints will be analyzed at 2 interim analyses and the final analysis. The interim analyses will be conducted by the independent statistical team and reviewed by the independent DMC. The Lan-DeMets/O'Brien-Fleming alpha(α)-spending function ([Lan 1983, O'Brien 1979](#)) will be used to control the overall Type I error at one-sided 0.025 level. At each analysis, VE will be summarized by the one-sided $(1-\alpha)100\%$ CI. The table below summarizes the

information fraction (ie, % of total cases), nominal α , criterion for success, and cumulative probability of success if the true VE is 60% for each analysis:

Analysis	Information Fraction (% of Total Cases)	α	Success Criterion	Cumulative Probability of Success (if true VE=60%)
Interim #1	40% (64 cases)	0.0004	Point estimate of VE \geq 50% and lower bound of the one-sided 99.96% CI for VE is $>$ 30%	9.9%
Interim #2	70% (112 cases)	0.0073	Point estimate of VE \geq 50% and lower bound of the one-sided 99.27% CI for VE is $>$ 30%	61.5%

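### The sample-size re-estimation rule sets the placebo rate at 64 cases against a 1.3% that fits only the 160-case final analysis, so a trial on plan can trigger it

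*Combined protocol and SAP*

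**What the plan says.** All of this is in the combined protocol and SAP, Statistical Methods.

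- **Sample Size, case target:** "the primary efficacy analysis will require ~160 confirmed COVID-19 illness cases which will provide 90% power", for a true VE of 60% against a null of 30%.
- **Sample Size, conversion to subjects:** "Assuming the placebo illness rate is 1.3%, ~17,600 subjects will be required in the evaluable efficacy population for the primary efficacy analyses". No follow-up period or person-time unit is attached to the 1.3%.
- **Sample Size, reason for checking the rate:** incidence may change during the pandemic. A rise would bring cases sooner, "whereas a decrease in illness rate could slow down case accrual delaying the evaluation".
- **Sample Size, trigger at the first interim efficacy analysis:** "If the upper bound of the two-sided 95% CI for the observed placebo illness rate is less than the assumed placebo illness rate".
- **Sample Size, consequence:** "then the sample size will be re-estimated by the independent statistician and DMC based on the observed placebo illness rate", with "recommendations made to the Sponsor for final decision by the Sponsor".
- **Primary Efficacy Analysis table:** the first interim is at 64 cases (40% of information) and the final analysis at 160.

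The text does not define the denominator of the observed placebo rate, the confidence-interval method, or any adjustment for the shorter follow-up at the interim.

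**The concern.** The benchmark and the observation refer to different amounts of follow-up. The 1.3% describes the placebo arm when the trial has reached 160 cases. The rule applies it, unscaled, when the trial has reached 64.

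Because the interim is timed by total cases, the numerator is nearly fixed. A crude placebo proportion at that moment therefore depends mainly on how many subjects have entered the denominator, not on how fast cases arise. A trial that enrols quickly shows a low proportion even when incidence is exactly as planned. If a person-time rate is meant, the plan has no person-time figure to set it against.

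At stake is the re-estimated size. Where the rule fires for this reason, the calculation treats an interim proportion as the final one and returns too large an N. The independent statistician and DMC could then recommend enrolling many more subjects than the 160-case target needs.

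**Working it through.** **Inputs (Statistical Methods).** VE 60% (rate ratio 0.40); null VE 30%; one-sided alpha 0.025; 160 cases at the final analysis and 64 at the first interim; placebo rate 1.3%; 17,600 evaluable subjects, so 8,800 per arm; 15% unevaluable.

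**1. Reproduce the plan.** The exact conditional test with 160 cases at one-sided 0.025 has 91.2% power (stated 90%). Evaluable N = 2 x 160 / (0.013 x 1.4) = 17,582 (stated ~17,600). Randomized N = 17,600 / 0.85 = 20,706 (stated ~20,700). The design reproduces.

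**2. What the 1.3% means.** 8,800 x 0.013 = 114.4 placebo cases; x 1.4 = 160.2 in total. So 1.3% is the cumulative placebo proportion at the final analysis.

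**3. On-plan picture at the interim.** Expected placebo cases = 64 / 1.4 = 45.7, about 46. With all 8,800 counted, 45.7 / 8,800 = 0.52%, which is 40% of 1.3%.

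**4. When the rule fires (crude reading).** The exact Poisson upper 95% limit is 61.36 for 46 cases and 81.73 for 64.
- At the expected count: 61.36 / 0.013 = 4,720 placebo subjects, 53.6% of 8,800 (45.6% of the 10,350 randomized to placebo). Clopper-Pearson gives 4,713, Wilson 53.5% and Wald 51.8%.
- If all 64 cases were placebo cases: 81.73 / 0.013 = 6,287, or 71.4%. Above this the rule fires for every possible split.
- With the 64 cases split at random under VE 60%, it fires in 19% of trials at a 50% share, 58% at 54%, 97% at 60%, and essentially all at 70% or more.

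**5. Size of the recalculated N.** The on-plan crude rate is 0.4 x 1.3% / share, so the size factor is share / 0.4.

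| Share of 8,800 counted | Placebo rate, 46 cases (upper 95% limit) | Fires? | Size factor | Evaluable N |
|---|---|---|---|---|
| 50% | 1.05% (1.39%) | no | – | – |
| 60% | 0.87% (1.16%) | yes | 1.5 | 26,400 |
| 80% | 0.65% (0.87%) | yes | 2.0 | 35,200 |
| 100% | 0.52% (0.70%) | yes | 2.5 | 44,000 |

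The last row means 44,000 / 0.85 = 51,765 randomized.

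**6. How likely this is.** The documents give no enrolment pace, so this step rests on assumptions: constant hazard, with entry to the at-risk period spread over a fraction f of the time to the final analysis. The expected share at 64 cases is 1.0 for uniform entry with f = 0.5; 0.816 for f = 0.75; sqrt(0.4) = 0.632 for f = 1; and 0.4^(2/3) = 0.543 for linearly increasing entry with f = 1. Results from 2,000 simulated trials per scenario, 8,800 per arm, with the hazard set so that the placebo proportion at the final analysis is 1.3%:

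| Entry pattern | Fires, on plan | Median size factor | Fires, incidence 1.5 x plan |
|---|---|---|---|
| Uniform, f = 0.5 | 100% | 2.5 | 100% |
| Uniform, f = 0.75 | 100% | 2.0 | 99% |
| Uniform, f = 1 | 97% | 1.6 | 37% |
| Linear ramp, f = 1 | 55% | 1.35 | 1.5% |

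A person-time version, comparing the observed rate and its exact Poisson limits with the planned hazard, fires in 2.1% to 2.4% on plan, below 0.1% at 1.5 times plan, and at least 99.5% at half the planned incidence.

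**The case against.** The strongest reply is that the plan never says the rate is a crude proportion. It defines VE through an incidence rate ratio and sizes the trial under a Poisson assumption, which fits a rate reading. A careful statistician could also match follow-up periods or project to the final analysis, and nothing forbids that. This stands in part: the firing probabilities belong to the crude reading only. It does not rescue the rule, because on a person-time reading no planned rate exists to compare with, and the one quantity given is used as a proportion. A prespecified trigger should not rely on an unstated correction.

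A second point is that constant hazard is an assumption, and the plan itself expects incidence to change. If incidence falls linearly to half by the final analysis, with 1.3% still reached, on-plan firing drops to about 74% (uniform, f = 1) and 19% (ramp). If it falls by 75%, the figures are about 37% and 3%. With uniform entry over f = 0.75, firing stays at about 99%. The on-plan range is therefore roughly 3% to 100%. The 54% and 71% thresholds need no assumption about pace or hazard.

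Third, the outcome is a recommendation and the Sponsor decides. The 160-case target does not move, and extra subjects would only bring cases sooner. The factor of 2.5 needs every evaluable placebo subject to be in the denominator at the 64th case. All of this is fair and limits the weight of the point. Against it, the plan says the size will be re-estimated from the observed rate, so the inflated figure is what a literal reading produces.

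**Conclusion.** The concern holds and should be fixed before the first interim. As written, the rule does not test whether incidence is below plan. On the crude reading, a trial exactly on plan triggers it, at the expected case split, once more than about 54% of the 8,800 evaluable placebo subjects are counted. Above about 71% it triggers whatever the split. The recalculated N is then about 1.5 to 2.5 times plan for shares of 60% to 100%. On the person-time reading the comparison cannot be made from what the plan gives.

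The 54% figure rests on VE of 60%, an exact interval and the evaluable denominator. How often an on-plan trial would trigger depends on enrolment pace and the course of the epidemic, neither of which the documents fix. No effect on Type I error or on the VE estimate is claimed.

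**What to change.** 1. State the follow-up period behind the 1.3% and express it as placebo cases per person-time at risk, counted from 14 days after the last dose. Name the denominator population and the interval method.
2. Compare the observed placebo person-time rate and its 95% interval with that figure. Alternatively, compare the observed proportion with the cumulative placebo proportion expected at the first interim given actual enrolment and follow-up.
3. Base any re-estimated N on the placebo rate projected to the final analysis, with the assumed future incidence stated, and not on the interim cumulative proportion.

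The cost is protocol and SAP wording before the first interim. Person-time follows from vaccination and illness-onset dates and the follow-up contacts already scheduled. The 160-case target and the alpha spending do not change.

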The secondary primary endpoint is COVID-19 incidence based on central laboratory or locally confirmed NAAT in subjects with and without evidence of infection before vaccination.

Immunogenicity: Humoral immune response will be evaluated by S-binding IgG levels, N-binding IgG levels, and SARS-CoV-2 neutralizing antibody by cPass assay. Cellular immune response will be evaluated by SARS-CoV-2 specific memory CD4⁺ and CD8⁺ T-cell stimulation to N and S proteins.

Statistical Methods:

Primary Efficacy Endpoints: The first primary efficacy endpoint is COVID-19 incidence based on central laboratory or locally confirmed NAAT in subjects with no serological or virological evidence (up to 14 days after receipt of the last dose) of past SARS-CoV-2 infection and will be summarized in terms of $VE = 100\% \times (1 - IRR)$ [ratio of active vaccine to placebo].

After the above first primary endpoint is met, the second primary endpoint will be evaluated.

The second primary endpoint COVID-19 incidence based on central laboratory or locally confirmed NAAT in subjects with and without evidence of infection before vaccination.

Sample Size: The first 200 subjects randomized in the study will be included in phase 2. Phase 2 subjects will be included in the phase 3 portion of the study.

For phase 3, ~20,700 subjects will be randomized in a 1:1 ratio to either the hAd5-S-Fusion+N-ETSD or placebo. All randomized subjects who received at least one dose of study intervention will be included in the all-available efficacy population. The primary efficacy analysis will be based on the evaluable efficacy population which will include subjects in the all-available efficacy population who receive all planned doses of vaccine per schedule and have no major protocol deviations judged to effect efficacy.

The phase 3 sample size calculation is based on the primary efficacy endpoints and derived from the exact conditional test under the Poisson assumption which is appropriate for large trials where the illness rate is very low and hypothesis testing is based on a non-zero lower bound ([Chan 1998](#)). The null and alternative hypotheses for the primary efficacy analyses are:

Ho: $VE \leq 30\%$

Ha: $VE > 30\%$

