Final	100% (160 cases)	0.0227	Point estimate of VE \geq 50% and lower bound of the one-sided 97.73% CI for VE is $>$ 30%	90.0%

Should the primary endpoint(s) show success at either interim analysis, the Sponsor will decide after discussion with FDA to explore the options to expedite submission of the data for approval and possible early closure of the trial, with long-term follow up of patients already enrolled.

The study may be stopped early for futility (lack of benefit) at either interim analysis if the conditional power for the first primary endpoint is less than 5% ([Jennison 2000](#)).

A Poisson regression model with robust error variance will be used to estimate VE and its one-sided $(1-\alpha)100\%$ CI ([Zou 2004](#)).

Safety Analyses: Safety analyses will be based on the safety analysis population and subjects will be analyzed according to the actual study intervention received. Descriptive statistics will be provided for each reactogenicity endpoint for the active vaccine group and the placebo group. Local reactions and systemic events from Day 1 through Day 7 after each vaccination will be presented overall and by severity.

AEs and SAEs will be categorized according to the MedDRA terms. Descriptive statistics will be provided for each AE for the active vaccine group and the placebo group. For phase 2, AEs and SAEs will be presented for first vaccination through 7 days after last vaccination overall and by severity. For phase 3, AEs will be presented for first vaccination through 1 month after last vaccination and SAEs will be presented for first vaccination through 6 months after last vaccination overall and by severity.

Immunogenicity Analyses: Immunogenicity analyses will be based on the immunogenicity analysis population and subjects will be analyzed according to the actual study intervention received. Humoral immune response endpoints will be summarized descriptively for the vaccine and placebo groups by GMT, GMC, GMFR, percentage of subjects with titers greater than defined threshold(s), and neutralizing antibody titer demonstrated by ACE2 inhibition at baseline and specific times during the study, as noted in the Schedule of Events. Cellular immune response endpoints will be summarized

descriptively for the vaccine and placebo groups at baseline and specific times during the study, as noted in the Schedule of Events.

Figure 1: Study Schema

[figure not shown]

Table 8: Schedule of Events

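### Does re-estimating the sample size from the placebo-arm rate at the first interim analysis leak interim vaccine efficacy to the Sponsor?

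*Combined protocol and SAP*

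**What the plan says.** The combined protocol and SAP, under Statistical Methods (Sample Size), sets the planning values: 160 cases, true VE 60% against a null of 30%, one-sided 0.025. It continues: "Assuming the placebo illness rate is 1.3%, ~17,600 subjects will be required in the evaluable efficacy population". About 20,700 "subjects will be randomized in a 1:1 ratio to either the hAd5-S-Fusion+N-ETSD or placebo".

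The same section notes that incidence may change, "whereas a decrease in illness rate could slow down case accrual delaying the evaluation". It then sets the check: "At the time of the first interim efficacy analysis, the independent statistical team and DMC will evaluate the placebo illness rate". The trigger is worded: "If the upper bound of the two-sided 95% CI for the observed placebo illness rate is less than the assumed placebo illness rate". When it is met, the independent statistician and DMC redo the sample size "based on the observed placebo illness rate, and recommendations made to the Sponsor for final decision by the Sponsor".

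Primary Efficacy Analysis places the first interim analysis at 64 cases (40% information) and says: "The interim analyses will be conducted by the independent statistical team and reviewed by the independent DMC". The trial may stop for futility if conditional power for the first primary endpoint is below 5%. Study Design describes the trial as observer-blind.

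The text gives no re-estimation formula and no evaluable count at the first interim analysis, and it does not say what a recommendation to the Sponsor may contain.

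**The concern.** A placebo-arm rate in a blinded trial can be computed only with treatment codes. At the first interim analysis the total is 64 cases by design and allocation is 1:1. Anyone who knows the blinded evaluable count therefore knows the pooled rate, and the only new information in the placebo rate is how the 64 cases divide, which is interim VE. If the re-estimated size, or even the fact that re-estimation was triggered, reaches the Sponsor, the separation kept by the independent team and DMC could be partly undone. What would be at stake is operational bias in later conduct.

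There is also a question of fit. The stated worry is slow case accrual. With a 160-case target, accrual depends on the pooled rate, and a placebo rate needs an assumed VE to convert it.

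**Working it through.** **Plan's own figures.** Pooled rate = 0.013 × (1 + 0.4)/2 = 0.0091. Evaluable N = 160/0.0091 = 17,582 (plan: ~17,600). Randomized = 17,600/0.85 = 20,706 (plan: ~20,700). Both reproduce.

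**From case split to VE.** With k placebo cases out of 64 and equal arms, VE = 1 − (64 − k)/k = 2 − 64/k. So k = 40, 43, 46, 49 and 50 give VE 40%, 51%, 61%, 69% and 72%.

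**Yes/no trigger.** Assumptions: exact (Clopper-Pearson) two-sided 95% interval for k/n, and no projection for incomplete follow-up. The evaluable number per arm, n, is not in the documents. The smallest n at which the upper limit falls below 1.3% is:

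| k | VE | smallest n per arm |
|---|---|---|
| 32 | 0% | 3,469 |
| 40 | 40% | 4,183 |
| 43 | 51% | 4,448 |
| 44 | 55% | 4,537 |
| 50 | 72% | 5,063 |
| 64 | 100% | 6,278 |

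At the planned rate and VE 60%, 64 cases arise at about n = 64/(1.4 × 0.013) = 3,516. At n = 3,520 the trigger needs k ≤ 32. With k ~ Bin(64, 1/1.4) this has probability 0.00024. If n is allowed to vary with accrual, the trigger fires about 2% of the time when the placebo rate is 1.3%, whatever the VE.

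**Net of the interim decisions.** Using the exact conditional test at 0.0004, interim success needs k ≥ 51 (p = 0.00034; k = 50 gives 0.00092). Final success at 0.0227 needs 107 placebo cases out of 160. Conditional power under the current trend is 0.028 at k = 39 and 0.084 at k = 40. On this basis a continuing trial has k = 40 to 50 (VE 40–72%). The trigger result then adds information only for n of about 4,183 to 5,062. For example, at n = 4,500 it separates VE 40–51% (fires) from 55–72% (does not).

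**Exact new N.** If 160 cases and VE 60% are kept, N = 160/(0.7 × k/n). At n = 5,000, k = 40, 43, 46 and 49 give N = 28,571, 26,578, 24,845 and 23,324, a one-to-one map to VE. An error of 10% in n weakens it: for k = 40 the back-calculated k runs from 36 to 44, so VE runs from 2 − 64/36 = 22% to 2 − 64/44 = 55%. A pooled-rate N would be 160/(64/10,000) = 25,000 for every split.

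**What the pooled alternative costs.** Percentage of simulated trials in which re-estimation is triggered (200,000 runs per setting, constant placebo rate; pooled rule: upper limit below 0.91%):

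| Placebo rate | Rule | VE 0% | 30% | 40% | 60% | 90% |
|---|---|---|---|---|---|---|
| 1.3% | placebo | 2 | 2 | 2 | 2 | 2 |
| 1.3% | pooled | 0 | 0 | <1 | 2 | 48 |
| 0.9% | placebo | 55 | 62 | 65 | 70 | 79 |
| 0.9% | pooled | 2 | 27 | 45 | 82 | >99 |

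At a 0.9% placebo rate, 17,600 subjects yield 17,600 × 0.009 × 1.6/2 = 127 cases at VE 40% and 17,600 × 0.009 × 1.7/2 = 135 at VE 30%. Both fall short of 160, and there the pooled rule triggers less often than the plan's rule.

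**The case for a change.** The best case for a change is this. At VE 60% the window of 4,183 to 5,062 per arm corresponds to placebo rates of 64/(1.4n), or 1.09% to 0.90%. That is a fall of 16–31% from 1.3%, the kind of decline the rule was written for. An exact N is informative wherever the rule fires. A placebo-rate N can also miss its target: at 0.9%, N = 320/(0.009 × 1.4) = 25,397 yields 194, 160 or 137 cases at VE 30%, 60% or 80%. And the text puts no limit on what the Sponsor may be told.

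The arithmetic stands, and so does the silence on the content of the recommendation. The inference of a leak is weaker:

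- The text assigns evaluation of the rate and the re-estimation to the independent group. It does not say the Sponsor sees the rate or the case split. A Sponsor deciding on trial size after a DMC recommendation is ordinary practice.
- Evaluable counts depend on deviation rulings and, for the first primary endpoint, on serological and virological status, so the Sponsor's denominator is uncertain.
- The inversion formula is this review's assumption. A follow-up projection would break it.
- The window is soft. The futility rule is non-binding and its conditional-power basis is unstated; assuming VE 60% instead of the current trend gives 3,379 to 5,062. A large-sample log rate-ratio interval, closer to the plan's robust Poisson model, gives a lower bound of 27.8% at k = 51 and 32.5% at k = 52. Success then needs 52, and the upper edge moves to about 5,150.
- At a 0.9% placebo rate and VE 60%, the expected n is 64/(1.4 × 0.009) = 5,079, where every continuing split (k = 40 to 50) fires and the yes/no outcome says nothing.

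**Conclusion.** No change to the plan follows. A leak of interim VE is possible in principle, but only if the Sponsor knows the evaluable count closely and also learns either the trigger result in a limited range (about 4,200 to 5,100 per arm) or an exact N computed with the planning values held. The added signal is limited because the success and futility decisions already bound interim VE. At the planned accrual there is almost none: 0.02% firing at 3,520 per arm with VE 60%. Type I error is not inflated so long as 160 cases remain the target.

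Checking the plan's own placebo-rate assumption behind an independent team is a defensible choice. The pooled rate protects confidentiality better and relates directly to accrual, but it cannot tell low incidence from high VE. At a 0.9% placebo rate it triggers less often than the plan's rule at VE 40% (45% against 65%) and more often at VE 60% (82% against 70%). Neither rule is better throughout.

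What the text leaves open is a matter of DMC communication. A competent independent team would pass on a sample-size recommendation without the observed rate, and would keep the 160-case target on which the alpha spending rests. Following the plan in that way gives no wrong result. These conclusions rest on the exact interval, no follow-up projection, the exact interim test, current-trend conditional power with the futility rule followed, and assumed evaluable counts.

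### Interim #1: at 64 cases the robust-Poisson bound that decides success gives about a 5.1% chance of success at true VE 60%, not the tabulated 9.9%

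*Combined protocol and SAP*

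**What the plan says.** All places are in the Combined protocol and SAP, Statistical Methods.

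- **Looks and error control** (Primary Efficacy Analysis): "The primary efficacy endpoints will be analyzed at 2 interim analyses and the final analysis". A Lan-DeMets/O'Brien-Fleming spending function "will be used to control the overall Type I error at one-sided 0.025 level".
- **Success rule** (interim table): the VE point estimate must be at least 50%, and at Interim #1 the "lower bound of the one-sided 99.96% CI for VE is" required to exceed 30%. The later looks use 99.27% and 97.73% bounds.
- **Probability column**: introduced as the "cumulative probability of success if the true VE is 60% for each analysis", with entries 9.9%, 61.5% and 90.0% at 64, 112 and 160 cases.
- **Source of the bound**: "At each analysis, VE will be summarized by the one-sided" CI, and later in the same section, "A Poisson regression model with robust error variance will be used to estimate VE and its one-sided" CI.
- **Sample size**: a different method is cited. The calculation is "derived from the exact conditional test under the Poisson assumption which is appropriate for large trials where the illness rate is very low".
- **Consequence of interim success**: "Should the primary endpoint(s) show success at either interim analysis, the Sponsor will decide after discussion with FDA" whether to pursue expedited submission and possible early closure.

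The plan does not say which method produced the probability column.

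**The concern.** A reader takes the probability column to describe the success rule printed beside it. That rule uses the robust-Poisson bound. The sample size uses the exact conditional test, and the column appears to come from a third calculation. At 64 cases and alpha 0.0004 the rule sits far in the tail, where one vaccine case more or less changes the chance of success appreciably, so the three methods need not agree.

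What is at stake is how well the plan describes its first look. If the column overstates the chance of early success, the sponsor and the DMC start with the wrong expectation of a look whose success opens the discussion of early submission and closure.

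**Working it through.** **Inputs from the plan.** Null VE 30%, true VE 60%, 1:1 allocation, about 17,600 evaluable subjects (8,800 per arm), looks at 64/112/160 cases, one-sided alphas 0.0004/0.0073/0.0227. **Assumptions.** Equal follow-up and no covariates. Given the total, the vaccine count is then binomial with share 0.7/1.7 = 0.4118 under the null and 0.4/1.4 = 0.2857 at VE 60%.

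**1. Reproducing the plan's figures.** The spending function is 2[1 − Φ(2.2414/√t)] at t = 0.4, 0.7, 1. It gives nominal alphas 0.00039/0.0073/0.0227, as tabulated. With the drift set for 90% power (3.264), the first look gives Φ(3.264 × √0.4 − 3.357) = Φ(−1.29) = 9.8%. The three cumulative figures are 9.8/61.4/90.0%, against 9.9/61.5/90.0% stated. The column is therefore a normal-theory result.

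**2. The named bound at 64 cases.** With x vaccine cases of D, the lower bound for VE is 1 − exp{ln[x/(D−x)] + z·√[1/x + 1/(D−x) − 2/8800]}, with z = 3.353 for alpha 0.0004.

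- 12 v 52: ln ratio −1.466, SE 0.3199. Upper limit for the log ratio −1.466 + 1.073 = −0.394. Lower bound 32.5%: passes.
- 13 v 51: ln ratio −1.367, SE 0.3103. Upper limit −1.367 + 1.040 = −0.326. Lower bound 27.8%: fails.

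A fitted Poisson model with robust errors gives the same bounds. The condition VE ≥ 50% does not bind here (12 v 52 is 76.9%). The chance of success at VE 60% is P(X ≤ 12 | 64, 0.2857) = 5.05%.

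**3. The exact conditional test at 64 cases.** Under the null, P(X ≤ 13) = 0.00034 and P(X ≤ 14) = 0.00092, so the cutoff is 13 (lower bound 30.8%). The chance of success is P(X ≤ 13 | 64, 0.2857) = 8.97%. The split on which the two bounds differ, 13 v 51, has probability 3.92% at VE 60%. Its one-sided p is 0.00057 (robust) and 0.00034 (exact).

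**4. Splitting the gap.** The robust bound crosses 30% at an interpolated 12.55 vaccine cases. Smoothing the integer step gives 5.05% + 0.55 × 3.92% ≈ 7.2%. So about 9.9 − 7.2 = 2.7 points come from the bound and 7.2 − 5.1 = 2.1 points from discreteness.

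**5. All looks at the planned counts.**

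| | Cutoffs at 64/112/160 | Cumulative success at VE 60% | Overall one-sided error |
|---|---|---|---|
| Table | – | 9.9/61.5/90.0% | 0.025 |
| Robust Poisson | 12/33/53 | 5.1/62.8/91.5% | 0.0245 |
| Exact conditional | 13/33/53 | 9.0/62.9/91.5% | 0.0246 |

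**6. Nearby counts.** The plan says about 160 cases. With the table's alphas held fixed (an assumption) and looks at 64/112/159, the final cutoffs are 53 (robust) and 52 (exact), and overall one-sided error is 0.0277 and 0.0200. The split 53 v 106 shows why: VE is exactly 50% and the robust lower bound is 1 − exp(−0.6931 + 2.0009 × 0.1676) = 30.1%, which passes, although the null probability of 53 or fewer is 0.0259, above 0.0227.

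**7. Interim #1 away from 64 cases.** With alpha recomputed from the spending function at the actual fraction, it runs from 0.00025 at 60 cases to 0.00059 at 68. The chance of success over that range is 2.5% to 9.0% (robust) and 4.2% to 10.2% (exact).

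**The case against.** The strongest reply has three parts.

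- **The plan is not ambiguous about the deciding bound.** This stands. A reader might infer that 13 v 51 could be called either way, since two methods are named. The text does not support that: the exact conditional test is cited only for the sample size, and the CI in the success rule is assigned to robust Poisson regression. As written, 13 v 51 is a failure.
- **The 9.9% is a sound planning approximation, and no decision is taken from it.** This also stands. A reader might infer an arithmetic slip, but step 1 reproduces the column. What remains is that the figure is presented as the chance of meeting a stated criterion, and at the stated 64 cases that criterion gives about half of it.
- **Exact figures at single counts are points on a sawtooth, and the model's covariates are not specified.** This is fair. Step 7 shows how far Interim #1 moves with the count, and the 5.1% should carry that caveat. The 9.9% still lies above the whole robust range for 60 to 68 cases (2.5% to 9.0%).

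Two further inferences go too far in opposite directions. One is that the mismatch harms power or type I error in the design as planned: at 64/112/160 it does not. The other is that it is confined to Interim #1 and always conservative: step 6 shows that at 159 cases the robust bound is the more lenient one at the final analysis.

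**Conclusion.** The point holds and is minor. At exactly 64 cases and alpha 0.0004, the bound named in the plan gives about a 5.1% chance of success at true VE 60%, against 9.9% stated. The exact conditional test would give 9.0%.

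The result rests on 8,800 per arm, equal follow-up and no covariates; a smaller 3,520 per arm leaves the cutoff at 12. Confidence is high for the 64-case arithmetic and lower for any single figure at other counts. At the planned counts the later cutoffs agree, final power is about 91.5% and overall one-sided error is below 0.025. With the table's alphas held fixed, small departures from those counts can separate the two bounds at the final look and take the robust rule slightly above 0.025.

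**What to change.** Choose one of two edits in the Primary Efficacy Analysis section.

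1. **Keep the robust-Poisson bound.** Restate the Interim #1 probability as about 5% at 64 cases, and label the column as approximate and computed at the planned counts. On that basis the later entries are about 62.8% and 91.5%.
2. **Let the exact conditional bound decide success**, if that is what the sizing method was meant to imply. Name it in place of the robust-Poisson bound and give Interim #1 as about 9.0%. This also keeps the error at each look within its nominal alpha.

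In either case, any note on variation with the case count should recompute alpha from the spending function at the actual information fraction and cover all three looks. For Interim #1 at 60 to 68 cases it would read about 2.5% to 9.0% (robust) or 4.2% to 10.2% (exact).

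The cost is a sentence or two, a restated column and a less favourable Interim #1 figure. Alpha, case targets and the 20,700 subjects stay as they are.
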